National Taiwan University Hospital

Hsinchu Branch

Research Protocol 2018

1. Project name

Title	Prevalence and Outcomes of Peripheral Artery Disease in Sepsis Patients in the Medical Intensive Care Unit
Principal investigator	Department of Internal Medicine, Cardiovascular Division [name], Attending Physician

Table of Contents

1. Project name.....	1
2. Abstract.....	3
Background.....	3
Methods.....	3
3. Background.....	4
Prior research in this field.....	4
Sepsis and peripheral artery disease.....	4
Peripheral artery disease- its impact on the outcomes.....	4
Medications for treatment of PAD.....	4
Clinical needs.....	4
5. Goals of project.....	6
Purpose (for clinicaltrials.gov registration).....	6
Objectives.....	6
6. Methods and procedures.....	7
Research design.....	7
7. Anticipated results.....	10
8. Study progress plan.....	11
9. Assignment of Researcher.....	12
10. Funding.....	13

11. Reference.....	14
12. Appendix.....	15

2. Abstract

Background

The peripheral artery disease (PAD) has been well known for poor cardiovascular outcomes. Its prevalence is high in the elderly, in the diabetic patients, and in the patients receiving hemodialysis. To date, there is no guideline recommendation about screening of PAD in patients admitted to the medical intensive care unit (MICU) for sepsis.

Methods

We designed a prospective cohort study focusing on patients admitted to the MICU with the main diagnosis of sepsis. The ankle-brachial indexes are performed within 4 hours after admission. Invasive arterial line monitoring and standard non-invasive measurements are collected. After confirmation of PAD, standard anti-platelet treatments (aspirin and cilostazol) are initiated. The survival before and after the conduction of this trial is compared to historical records. The outcomes including all-cause mortality, stroke, myocardial infarction, minor amputation, major amputation, and prolonged ventilator dependent are to be collected.

Keywords: peripheral vascular disease, sepsis, outcomes

3. Background

Prior research in this field

Sepsis and peripheral artery disease

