Purpose (for clinicaltrials.gov registration)

- Study type: interventional
- Study Design:
 - Allocation: randomized - Endpoint classification: efficacy study - Intervention model: parallel - Masking: single blind (outcomes assessor) - Primary purpose: treatment
- Official title: as the study project title

Objectives

1. Perform a screening for PAD among patients admitted to the medical intensive care units and meet the sepsis diagnosis criteria (quick SOFA score ≥ 2 points).
2. Follow the outcomes (all cause mortality at 30 days, stroke, myocardial infarction, lower limb ischemia requiring amputation) of patients who have evidence of ABI < 0.9 or PAD by additional vascular Duplex confirmation.
3. To evaluate the prevalence of PAD among patients admitted to our intensive care units.
4. To obtain the diagnosis of PAD early on the admission day among multiple care teams (cardiologists, chest physicians, and critical care specialist) and to give adequate medical treatment as needed (anti-platelet agents).
5. To evaluate whether early diagnosis of PAD in sepsis patients will lead to decision-makings that will influence the patient's survival.
6. To evaluate whether early diagnosis of PAD will lead to decreased complications rate of invasive arterial line monitoring.

6. Methods and procedures

Research design

1. Research design: prospective cohort study
2. Locations: the medical intensive care units (MICU) of National Taiwan University Hospital, Hsinchu Branch.
Patient population: sepsis patients who meet the quick SOFA score ≥ 2 points.
3. The investigator is responsible of this research: [name].
4. Study parameters:
 1. The prevalence of PAD among patients admitted to the MICU with sepsis
 2. The outcomes of PAD patients presented with sepsis to the MICU
5. Research field: critical care medicine, cardiovascular disease, peripheral artery disease
6. Keywords: peripheral artery disease, sepsis
7. Study design: observational study (cohort study)
 1. Collection of data: prospective
 2. Inter rim analysis: yes
 3. Investigator manual: yes

2. Study population

1. Patient number: 200 patients
2. Age limitation: 20-100 years old
3. Inclusion criteria:
 1. Admission diagnosis with sepsis, meeting quick SOFA criteria ≥ 2 points (respiratory rate $\geq 22/\text{min}$, altered mentation, systolic blood pressure $\leq 100 \text{ mmHg}$, each item is one point)
 2. Within the study age limitation
 3. Willing to participate the study
4. Exclusion criteria:

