1. This research will not require a paper inform consent. Because this study has minimal risk for the study participant- the ABI study was non-invasive. And this study will be carried in the medical intensive care units, it is focused on emergency medicine. The patients with sepsis admitted to the MICU usually are already in a critical condition and there is a need to aggressively diagnose any disease that will lead to poor outcomes. The benefits of diagnosing a PAD early outweigh the risk carried by the study method.

6. The study method

1. After enrollment, within 24 hours: the nurse will measure the ankle-brachial index (ABI). The measurements are to be done by A-line at any arteries that physician considered appropriate and additional bilateral lower limb blood pressure measurements. A Doppler scanner is allowed to be used to facilitate the measurement of ABI.
2. The definition of ABI (ankle-brachial index): the leg systolic blood pressure divided by the higher readings of bilateral brachial artery. If ABI < 0.9, a diagnosis of PAD is made.

7. The follow-up

1. At the time of admission: APACHE score
2. The treatment patient received: ventilator, vasopressor, inotropic agent, blood pressure, and the diagnosis.
3. Patient will be followed at 7 days, 30 days, and 90 days.
4. Medications will be recorded, especially: aspirin (Bokey), cilostazol (Pletal), clopidogrel (Plavix), statin.
5. Clinical events will be documented:
 1. Mortality
 2. Acute myocardial infarction
 3. Stroke, ischemic
 4. Limb gangrene resulting in amputation

8. Statistical method

1. We plan to enroll 200 patients. Patients will be grouped into patients with PAOD and patients without PAOD. We then compare them in the following parameters: clinical data, laboratory data, survival and other outcome data. Two-sample student's t tests will be used for the comparisons of continuous variables. Chi-square test will be used to detect difference between categorical variables. Difference is considered statistically significant if $P < 0.05$. All statistics works were analyzed using the SPSS 17.0 software (Chicago, IL, USA), R software (Gimc packages).

7. Anticipated results

1. Evaluate the care process and quality in patients in the MICU
2. Evaluate the prevalence of PAD in patients with sepsis admitted to the MICU
3. Investigate the influence of PAD to the outcomes of sepsis

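### Outcomes with and without PAD are compared by unadjusted tests only, so the contrast cannot support the stated aim on the influence of PAD, although age and admission APACHE are available for adjustment

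*Combined protocol and SAP*

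**What the plan says.** Section 6, item 8 (Statistical method) plans 200 patients, divides them by the presence of PAOD (read here as PAD) and states: "We then compare them in the following parameters: clinical data, laboratory data, survival and other outcome data". Continuous variables get a two-sample t test. For the rest, "Chi-square test will be used to detect difference between categorical variables", with significance at P < 0.05. Neither this item nor any other section names a regression, a stratification, a matching method or an adjustment covariate. SPSS and R are named, but no model is.

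PAD is diagnosed from the ankle-brachial index (Section 6, item 6): "If ABI < 0.9, a diagnosis of PAD is made". Objective 2 in Section 5 adds a second route, Duplex confirmation, and lists the outcomes: "Follow the outcomes (all cause mortality at 30 days, stroke, myocardial infarction, lower limb ischemia requiring amputation".

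The first follow-up entry (Section 6, item 7) is "At the time of admission: APACHE score". Age is an entry criterion. The Abstract says of PAD: "Its prevalence is high in the elderly, in the diabetic patients, and in the patients receiving hemodialysis". Section 7, item 3 gives the influence of PAD on sepsis outcomes as an anticipated result.

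**The concern.** The two groups differ by a diagnosis and not by allocation. By the protocol's own account, patients with PAD are more likely to be old, diabetic or on dialysis, and each of these may plausibly affect death in sepsis. A crude chi-square test mixes any association of PAD with death with these differences and with differences in admission severity. A P value below 0.05 could then be read as an influence of PAD when PAD contributes nothing. An imbalance in the other direction could hide a real association.

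Two of the relevant covariates, age and admission APACHE, are already in hand. If the covariates are left to be chosen after the outcomes are known, the choice can follow the data.

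**Working it through.** **Plan's own figure.** The only figure is 200 patients. It comes without an effect size, power, mortality or expected PAD prevalence in sepsis, so there is nothing to reproduce. The bias cannot be derived from the documents either. Both steps below illustrate it over assumed inputs, with no true PAD effect throughout.

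**Inputs.** From the documents: n = 200; alpha 0.05 (two-sided assumed); PAD prevalence 30% or 48%, which Section 3 gives for haemodialysis patients and which serves here only as a range. Everything else is assumed.

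**Step 1, by hand.** Let severity be high or low, with mortality 15% if low and 50% if high. High severity is present in 60% of PAD and 40% of other patients.

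- PAD mortality: 0.4 × 0.15 + 0.6 × 0.50 = 0.36.
- No-PAD mortality: 0.6 × 0.15 + 0.4 × 0.50 = 0.29.
- Crude OR: (0.36/0.64) / (0.29/0.71) = 1.38.
- At 30% prevalence (60 v 140 patients), pooled mortality is (60 × 0.36 + 140 × 0.29)/200 = 0.311.
- SE under the null: √[0.311 × 0.689 × (1/60 + 1/140)] = 0.0714. SE under the alternative: √[0.36 × 0.64/60 + 0.29 × 0.71/140] = 0.0729.
- P(reject) = Φ[(0.07 − 1.96 × 0.0714)/0.0729] + Φ[(−0.07 − 1.96 × 0.0714)/0.0729] = 0.168 + 0.002 = 0.17.

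With mortality 20%/40% or 15%/50% and high severity in 60% v 40% or 65% v 35%, the crude test rejects in 9% to 35% of studies. A Mantel-Haenszel test stratified on severity rejects in 4.8% to 5.2% in every simulated case (40,000 replicates each).

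**Step 2, the model proposed here.** Severity and age are continuous (SD 1 within group, correlation 0.3), and PAD patients have the same gap in both. APACHE measures severity with reliability 0.5 or 0.7. The death model is

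logit P(death) = logit(0.25) + ln(2.0) × severity [+ ln(1.3) × age] [+ ln(1.3) × diabetes + ln(1.8) × haemodialysis].

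Case 1 uses severity only, case 2 adds age, and case 3 adds all terms (diabetes 50% v 35%, haemodialysis 20% v 10%, base mortality 22%). With a gap this gives about 55–65 deaths. The crude test is chi-square without continuity correction; the adjusted test is the logistic Wald test for PAD with APACHE and age.

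| Case | Gap (SD) | Crude rejects (OR) | APACHE + age rejects (OR) |
|---|---|---|---|
| 1 | 0.25 | 7–9% (1.15–1.19) | 4–6% (1.02–1.07) |
| 1 | 0.5 | 15–18% (about 1.4) | 4–7% (1.06–1.14) |
| 2 | 0.25 | 10–11% (1.22–1.25) | 5–6% (1.02–1.07) |
| 2 | 0.5 | 25–30% (1.51–1.55) | 5–8% (1.06–1.15) |
| 3 | 0.25 | 15–18% | 6–8% (1.14–1.19) |
| 3 | 0.5 | 33–39% | 8–10% (1.19–1.25) |

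With no gap, cases 1 and 2 give 4–6% for both tests. In case 3, adding diabetes and haemodialysis to the model gives 5–6% (OR 1.03–1.08) and 6–7% (OR 1.08–1.13).

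**Step 3, feasibility.** The main model has three terms (PAD, APACHE, age): 55/3 = 18 to 65/3 = 22 deaths per term. The sensitivity model has five: 55/5 = 11. At an assumed 5% frequency, stroke, infarction or amputation gives 200 × 0.05 = 10 events, or 10/3 = about 3 per term, too few for this model.

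**The case against.** **The aim is descriptive.** None of the six objectives asks for an effect of PAD against no PAD, and the listed study parameters are prevalence and the outcomes of PAD patients. Unadjusted figures serve these well. This stands, and it limits the point to the anticipated result on influence. Withdrawing that wording would also resolve it.

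**APACHE may not be a pure confounder.** PAD is chronic and precedes admission, so admission severity may partly lie between PAD and death. Adjusting for it could remove part of a total effect. The simulations assume no PAD effect and cannot test this. It stands, and it is why an age-only estimate is needed as well.

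**APACHE may be compared as clinical data.** It may well be tabulated by group, but tabulation shows an imbalance and does not correct the outcome comparison for it.

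**The registration text says randomised.** A reader might infer that this protects the comparison. PAD status cannot be allocated, and Section 6 describes an observational cohort without a control group.

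**Stronger readings.** A reader might infer that the planned comparison will be biased by a known amount. The documents give no imbalance, mortality or covariate effects, so neither size nor direction is established. A reader might also infer that age and APACHE would isolate the effect of PAD. Case 3 shows they need not. The estimate would also include any antiplatelet treatment given after diagnosis, and the documents are not consistent on that: the Abstract says it is initiated once PAD is confirmed, while Objective 4 says as needed.

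**Conclusion.** The point holds for one use of the data. An unadjusted contrast between groups formed by diagnosis cannot support a statement about the influence of PAD on sepsis outcomes, and the plan offers no other analysis. That omission is plain from the text. The prevalence estimate and the description of outcomes in PAD patients are not affected.

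The size is illustrative only. It rests on no true PAD effect, 200 patients, about 55–65 deaths, and an assumed gap of 0.25 to 0.5 SD in age and severity. Across the three cases the nominal 5% error of the crude test becomes about 7–9% at the mildest and 33–39% at the worst. At the smaller gap in case 1 the excess is only a few percentage points. Age and APACHE recover most of the loss but leave an OR of about 1.14–1.25 in case 3, so the adjusted result would still be an association with residual confounding.

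**What to change.** Amend the Statistical method item as follows.

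1. Make the main comparison by PAD status a logistic regression of 30-day all-cause mortality on PAD, with age and admission APACHE as prespecified covariates.
2. Define PAD as in Objective 2, by ABI below 0.9 or by Duplex. Include patients alive at PAD assessment who can be classified by either route, and report earlier deaths and unclassified patients separately. The assessment window needs to be settled for this, since the Abstract says "The ankle-brachial indexes are performed within 4 hours after admission" and Section 6, item 6 says "After enrollment, within 24 hours: the nurse will measure the ankle-brachial index (ABI)."
3. Show the age-only adjusted estimate alongside, and describe the APACHE-adjusted one as the association of PAD at a given admission severity.
4. Add diabetes and haemodialysis in one prespecified sensitivity model if they are available at baseline; the plan does not list them as collected.
5. Keep the t and chi-square tests as unadjusted description, including for stroke, infarction and amputation, and draw no conclusion on influence from them.
6. Report the adjusted OR with its 95% CI as an association that includes any antiplatelet treatment given after diagnosis, and state residual confounding. The Abstract and Objective 4 must be reconciled on that treatment.

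The cost is SAP wording and a little analysis time in software already named. The main model needs no new data. In simulation the standard error of the log OR is about 3–10% larger than crude, and 7–13% larger with diabetes and haemodialysis added.
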